3.3 Study Duration

Participants will be on study for up to 18 weeks (4 weeks of screening, 12 weeks of treatment with study drug and 2 weeks of follow up).

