6 STUDY TREATMENTS

6.1 Description of Treatments

160 mg of PLN-74809 or matching placebo administered orally QD (2 tablets)

PLN-74809 and matching placebo will be supplied by Pliant as a tablet for oral administration. Study drug will be taken once daily at approximately 24-hour intervals.

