6.2 Dose Modifications and Interruptions

There will be no dose modifications of the study drug. If the study drug needs to be interrupted for safety or tolerability issues, this should happen, as feasible, in consultation with the Sponsor Study Director, who together with the Investigator will assess and decide whether the study drug interruption should be temporary or permanent on a case by case basis. Participants who discontinue study drug for safety reasons prior to completion of 12 weeks of treatment will be asked to remain in the study to complete all remaining assessments; if this is not feasible, then they will be asked to return to the clinic for an early termination visit.

Dose modifications or interruptions of pirfenidone or nintedanib treatment may be implemented only for safety and tolerability reasons (e.g., liver enzyme elevation; see [Section 9](#)), in accordance with their corresponding prescribing information and in consultation with the Sponsor Study Director. This should not affect the administration of the study drug or the continuation of participants in the study.

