1 INTRODUCTION

This document details the planned statistical analyses for Pliant Therapeutics Inc, protocol “PLN-74809-IPF-205” study titled “A Phase 2a, randomized, double-blind, placebo-controlled evaluation of PLN-74809 on type 1 collagen deposition using ⁶⁸Ga-CBP8 PET/MRI imaging in participants with idiopathic pulmonary fibrosis (IPF)”. The proposed analyses are based on the contents of Amendment 1 of the protocol (dated 04 Oct 2021). Any changes made from the planned analysis described in the protocol or after finalization of this SAP will be documented in the Clinical Trial Report (CTR).

This is a Phase 2a, single-center, randomized, double-blinded, placebo-controlled study to evaluate type 1 collagen deposition in the lungs following once-daily treatment with 160 mg PLN-74809 for 12 weeks in participants with IPF. The study consists of an up to 28-day screening period, a 12-week treatment period, and a 2-week (± 3 days) post treatment follow-up period.

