- If the stop date occurs on or after the start of study drug or the event / concomitant medication is ongoing, and the year is the same as the year of first dosing, the start date will be imputed as the date of the first dose of study drug. If the year is different from the year of first dosing, "01-Jan" will be used.
- If the stop date occurs before the start of study drug, the start date of the event / concomitant medication will be imputed as the "01-Jan" of the same year.

Partial start date (month and year present, but day missing)

- If the stop date occurs on or after the start of study drug or the event / concomitant medication is ongoing, the start date will be imputed as the first day of the same month and year unless this partial start date is in same month as the first dose of study drug in which case the date of first dose of study drug will be used.

QMD Ref. [REDACTED]	Governing QMD: [REDACTED]
Confidentiality Statement	
This document is the property of [REDACTED] and may not be duplicated, copied, altered or removed from company without prior approval from [REDACTED] or in compliance with [REDACTED]	

		Controlled Quality Management Document	
		Sponsor:	Pliant Therapeutics Inc
		Protocol Number:	PLN-74809-IPF-205
STATISTICAL ANALYSIS PLAN			

- If the stop date occurs before the start of study drug, the start date will be imputed as the first day of the month and year of the partial stop date.

If the start time is missing it will be imputed only in the case where the start date of the concomitant medication / event corresponds to the date of the first dose of study drug. The time will be imputed as the same time as the first dose of study drug. In all other cases the time will not be imputed.

Missing Date of Last Dose

If date of last dose is not present, the date of completion/termination will be imputed as the date of last dose for the calculation of study drug exposure.

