5.2.11 Exposure to Study Drug

Exposure to study drug will be calculated as follows:

$$\text{date of last dosing} - \text{date of first of dosing} + 1$$

The exposure calculation will not take into account breaks in therapy.

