5.2.12 Study Drug Compliance

Study drug compliance will be calculated by comparing the amount of drug dispensed and drug returned for each participant as follows:

Number of tablets taken = Total dispensed – Total returned (if the number returned is missing, a value of 0 will be used).

Expected number of tablets = Number of days on study (calculated as per Section 5.2.9 for duration of exposure) \times Number of tablets for the treatment group (per the table below).

PLN-74809	2 \times 80-mg tablets per day
Placebo	2 tablets per day

Compliance (%) = (Number of tablets taken / Expected number of tablets taken) \times 100.

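### The SAP's fallback for a missing last-dose date has no cap at the end of dosing, so it can count off-drug follow-up as exposure

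*SAP*

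**What the plan says.** For a missing last-dose date, SAP 5.2.10 states that "the date of completion/termination will be imputed as the date of last dose for the calculation of study drug exposure". It does not say whether completion refers to the drug or the study, and it sets no upper limit at the end of treatment.

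SAP 5.2.11 defines exposure as last-dose date minus first-dose date plus 1, and adds: "The exposure calculation will not take into account breaks in therapy".

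SAP 5.2.12 divides tablets taken by expected tablets. Expected tablets are two per day multiplied by "Number of days on study (calculated as per Section 5.2.9 for duration of exposure"). SAP 5.2.9 defines study day; exposure is defined in 5.2.11. For tablets taken, "if the number returned is missing, a value of 0 will be used".

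On timing, SAP 1 describes "a 12-week treatment period, and a 2-week (± 3 days) post treatment follow-up period", and Protocol 3.3 gives the same structure: "4 weeks of screening, 12 weeks of treatment with study drug and 2 weeks of follow up". Protocol Appendix 1 puts the Week 12 visit at Day 84 ±3 and the end-of-study visit at Day 98 ±3. Its footnote j has study drug taken in clinic at Visits 3, 5 and 8, and at an early termination (ET) visit where one applies. Under Protocol 6.2, participants who stop drug early for safety reasons "will be asked to remain in the study to complete all remaining assessments".

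**The concern.** Dosing is planned to end about two weeks before the study does. A fallback that replaces the last dose with the end of the study therefore adds days on which no drug was scheduled. If the study date is meant, it cannot precede the last dose, so the error is zero or positive and does not average out across participants.

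The gap is widest for participants who stop drug early and remain for follow-up, as the protocol asks of those who stop for safety reasons. Extent of exposure is the context in which a reader interprets the safety data, and safety is the secondary objective. With about 8 active and 4 placebo participants, one wrong value visibly moves an arm mean. The longer duration may also enter the compliance denominator.

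**Working it through.** **Inputs**
- Week 12 visit, Day 84 ±3, and end-of-study visit, Day 98 ±3 (Protocol Appendix 1).
- Follow-up of 2 weeks ±3 days (SAP 1).
- Two tablets a day (Protocol 6.1).
- Exposure and compliance formulas (SAP 5.2.11, 5.2.12).
- Arm sizes of 8 and 4 (SAP 3).

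**The plan's own figures.** Day 98 − Day 84 = 14 days, which matches the stated 2 weeks; 4 + 12 + 2 = 18 weeks, which matches Protocol 3.3.

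**Which completion?** SAP 5.4 counts completing the drug and completing the study separately, and attaches early termination to the study. The SAP 5.12.1 summaries by system organ class pair termination with the study and discontinuation with the drug. This favours the study reading but does not settle it. The figures below assume it.

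**Formulas.** With the first dose on Day 1, exposure equals the day number of the last dose. Overstatement = imputed ÷ true − 1. For someone who takes every dose up to the true last day, compliance = (2 × true days) ÷ (2 × imputed days), *if* imputed exposure is the denominator.

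| Case | True last day | Imputed day | Gap (days) | Overstatement | Compliance of a perfect adherer |
|---|---|---|---|---|---|
| Completer, nominal | 84 | 98 | 14 | 98/84 − 1 = 16.7% | 168/196 = 85.7% |
| Completer, follow-up 2 weeks − 3 days | 84 | 95 | 11 | 13.1% | 88.4% |
| Completer, follow-up 2 weeks + 3 days | 84 | 101 | 17 | 20.2% | 83.2% |
| Completer, shortest gap with both windows free | 87 | 95 | 8 | 9.2% | 91.6% |
| Completer, longest gap with both windows free | 81 | 101 | 20 | 24.7% | 80.2% |
| Stops Day 42, stays to Day 98 (assumed) | 42 | 98 | 56 | 133.3% | 42.9% |
| Stops Day 28, stays to Day 98 (assumed) | 28 | 98 | 70 | 250.0% (3.5 times) | 28.6% |
| Early terminator dosed at an ET visit on Day 42 (assumed) | 42 | 42 | 0 | 0% | 100% |

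**Effect on arm means.** One affected nominal completer raises mean exposure by 14/8 = 1.75 days in the active arm or 14/4 = 3.5 days on placebo. If the compliance denominator follows, mean compliance falls from 100% to (7 × 100 + 85.7)/8 = 98.2%, or (3 × 100 + 85.7)/4 = 96.4%.

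**Compliance under other readings**
- If days on study is taken literally, a nominal completer has 2 × 98 = 196 expected tablets and shows 168/196 = 85.7% after perfect adherence, *even when the last-dose date is present*.
- If the return count is also missing, all dispensed tablets count as taken. The documents do not give the number dispensed. Against 196 expected, an assumed 180 gives 91.8%, 196 gives 100% and 210 gives 107.1%, so the direction can reverse.

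**The case against.** The strongest case against the point has four parts.

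- **The wording is ambiguous, not plainly wrong.** If treatment completion was meant, the bias largely disappears for completers. That stands as a caveat. But a programmer could implement either reading, and the SAP's own usage leans towards the study.
- **The rule may rarely be triggered.** On-site doses are taken in front of staff and home doses are logged (Protocol 5.4). Dosing times must be recorded with PK samples, which include Week 12 (Protocol 7.9). Last-dose dates go into the eCRF when drug is interrupted because a liver or QTc finding cannot be evaluated promptly (Protocol 9 and 10). This stands: the documents give no basis for estimating how many dates will be missing, and it may be none.
- **Little depends on the result.** Exposure and compliance are summarised descriptively (SAP 5.9, 5.10). AE percentages use the number of participants (SAP 5.3.3), and the treatment-emergent window runs to the last study visit (SAP 5.12.1). The primary ANCOVA (SAP 5.11.1) does not use the last-dose date. This stands too.
- **The termination date is sometimes correct.** Footnote j of Protocol Appendix 1 allows a dose at the ET visit. A blanket ban on that date would therefore be wrong.

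A reader might also infer that the imputed date is always at least two weeks late. The documents do not support that: two weeks is the nominal gap, and the windows allow 8 days for a completer. Nor do they support a flat statement that compliance is understated. SAP 5.2.10 states the imputation only for exposure, SAP 5.2.12 points elsewhere for its day count, and zero-filling missing returns pushes compliance upward.

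**Conclusion.** The point holds in limited form. Assuming completion/termination refers to the study, the rule overstates exposure for any completer with a missing last-dose date: 98 days instead of 84, or 16.7% (9.2% to 24.7% across the windows). The overstatement can reach several-fold for someone who stops drug early and stays, and is zero for an early terminator dosed at the termination visit.

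The fall in compliance to 85.7% follows only if imputed exposure is the denominator. Separately, the reference to SAP 5.2.9 and the days-on-study wording are a defect of their own, because read literally they lower compliance for every completer.

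The consequences of the imputation are confined to descriptive summaries for participants whose date is missing, a number the documents do not give. Nothing here shows that a safety conclusion would change, and the primary SUV result is unaffected. It is still worth correcting, because a stated rule yields a wrong figure that a small edit avoids.

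**What to change.** 1. In SAP 5.2.10, impute a missing last-dose date from the last documented dose (in-clinic dosing record or dosing log). If there is none, use the earliest available of the recorded drug-discontinuation date, the Week 12 visit date and the study termination date. As a fallback, the termination date then applies only when it falls before Week 12.
2. In SAP 5.2.12, change the cross-reference from 5.2.9 to 5.2.11, and base expected tablets on days of exposure instead of days on study.

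For the nominal completer this restores 84 days and 168/168 = 100%. One limit remains: someone who stops early and stays, with neither a documented dose nor a discontinuation date, would still be assigned the Week 12 visit date, but follow-up time would no longer be counted.

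The cost is a few sentences in the SAP and a small programming change, with little or no new data. The protocol does not say that home dosing-log entries reach the analysis database. If they do not, the in-clinic records and the fallback dates would have to serve.

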5.2.11 Exposure to Study Drug

Exposure to study drug will be calculated as follows:

$$\text{date of last dosing} - \text{date of first of dosing} + 1$$

The exposure calculation will not take into account breaks in therapy.

5.2.12 Study Drug Compliance

Study drug compliance will be calculated by comparing the amount of drug dispensed and drug returned for each participant as follows:

Number of tablets taken = Total dispensed – Total returned (if the number returned is missing, a value of 0 will be used).

Expected number of tablets = Number of days on study (calculated as per Section 5.2.9 for duration of exposure) \times Number of tablets for the treatment group (per the table below).

PLN-74809	2 \times 80-mg tablets per day
Placebo	2 tablets per day

Compliance (%) = (Number of tablets taken / Expected number of tablets taken) \times 100.

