5.4 Treatment Compliance

Dosing will be performed in the presence of site staff every time the participant is on site on dosing days. For offsite dosing, participants will be provided with a dosing log in which they will collect dosing information for PLN-74809 and, if applicable, nintedanib or pirfenidone doses taken at home. Participants should return all used and unused medication bottles to the site at each site visit.

Treatment compliance will be calculated comparing the amount of drug dispensed and drug returned.

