5.2.9 Duration / Study Day / Time

Study day will be calculated as the number of days from first dose of study drug

- date of event – date of first dose of study drug + 1, for events on or after first dose
- date of event – date of first dose of study drug, for events before first dose

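### SAP 5.2.12 replaces a missing returned-tablet count with zero, so reported compliance can only err upward; the denominator's label and cross-reference also need correcting

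*SAP*

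**What the plan says.** **Numerator.** SAP 5.2.12 takes total tablets dispensed minus total returned. For an absent count, "if the number returned is missing, a value of 0 will be used".

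**Denominator.** "Expected number of tablets = Number of days on study (calculated as per Section 5.2.9 for duration of exposure"), multiplied by two tablets per day in either arm. The section it cites, SAP 5.2.9, defines the study day of an event: "Study day will be calculated as the number of days from first dose of study drug". The exposure formula itself (last dose minus first dose plus 1) is in SAP 5.2.11.

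**Collection.** Protocol 5.3 requires used and unused bottles back at Weeks 4, 8 and 12. The Schedule of Events has accountability at those visits and at the Week 14/early termination visit. Protocol 5.4 bases compliance on dispensed against returned drug, and also sets up a second record: "For offsite dosing, participants will be provided with a dosing log in which they will collect dosing information for PLN-74809". The SAP formula does not use that log.

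**Use.** SAP 5.10 summarises compliance descriptively in the safety population. No analysis population and no model described in the SAP depends on it.

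**The concern.** A missing return count means that nobody knows how many tablets were left. Zero is the one value that assumes none were. Since a participant cannot take more than was dispensed, the substitution is either exactly right (the bottle was empty) or too high; it is never too low. It also sits badly with Protocol 7.14, under which missed assessments are recorded as missed and left unimputed.

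Adherence matters to interpretation here. Exposure under SAP 5.2.11 is first to last dose, and "The exposure calculation will not take into account breaks in therapy", while the PD population admits anyone who received any study drug and has the required results. The compliance table is therefore the planned summary in which missed home doses over the 12 weeks would show. With about 8 and 4 participants, one wrong value is visible in an arm's mean and minimum.

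The denominator is a separate, smaller matter. It is labelled as time on study, qualified as duration of exposure, and referred to a section that names no end date. Two programmers could derive it differently.

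**Working it through.** Neither document states a compliance figure or threshold, so there is none to reproduce. The SAP formula is applied directly:

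compliance (%) = 100 × (dispensed − returned) / (days × 2)

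**Inputs**
- Two tablets daily: "160 mg of PLN-74809 or matching placebo administered orally QD (2 tablets"), Protocol 6.1, and the table in SAP 5.2.12.
- 84 treatment days, with dispensing on Day 1, Week 4 and Week 8 (Schedule of Events). Expected tablets: 84 × 2 = 168.
- Tablets per dispensing: not stated. **Assumption:** 56 (28 × 2, an exact supply), with a range up to 70. Visit windows of ±2 to ±3 days make some overage plausible.

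Check: all 168 tablets taken over 84 days gives 168/168 = 100.0%.

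**Third bottle not returned, first two (112 tablets) fully taken**

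| Taken from third supply of 56 | True compliance | Reported, bottle of 56 | Reported, bottle of 60 | Reported, bottle of 70 |
|---|---|---|---|---|
| 0% | 112/168 = 66.7% | 168/168 = 100.0% | 172/168 = 102.4% | 182/168 = 108.3% |
| 50% (28 tablets) | 140/168 = 83.3% | 100.0% | 102.4% | 108.3% |
| 80% (44.8 tablets) | 156.8/168 = 93.3% | 100.0% | 102.4% | 108.3% |
| 100% | 168/168 = 100.0% | 100.0% | 102.4% | 108.3% |

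The reported value does not depend on what was taken from that bottle.

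**Early stop.** Last dose on Day 42, every dose taken, second bottle of 56 not returned. True: 84/84 = 100%. Reported on exposure days: 112/84 = 133.3%.

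**Effect on an arm mean.** The half-taken case is wrong by 100.0 − 83.3 = 16.7 points. That moves the mean by 16.7/8 = 2.1 points in an arm of 8, or 16.7/4 = 4.2 points in an arm of 4.

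**Denominator, fully adherent completer**
- SAP 5.2.11, last dose on Day 84: 168/(84 × 2) = 100.0%.
- SAP 5.2.9 formula with last dose as the event: also 84 days, so 100.0%.
- Literal days on study to Week 14 (Day 98): 168/(98 × 2) = 168/196 = 85.7%. For Days 95 to 101, the range is 88.4% to 83.2%.

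**After the fix, half-taken case**
- Dosing log available: (112 + 28)/168 = 83.3%.
- Log unavailable, interval set to missing: 112/112 = 100% over 56 days. This does not recover the true value, but it no longer makes a claim about the unobserved interval, and the participant is counted among those with incomplete data.

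**The case against.** **The rule is a fallback with limited reach.** Bottle return is mandatory, accountability is scheduled, and doses on clinic dosing days are taken in front of staff. The documents give no expected frequency of missing counts. This stands: the error arises only when a count is missing and tablets remained.

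**Some errors announce themselves.** With overage or an early stop, the result exceeds 100%. That is true, but with an exact supply it reads as an unremarkable 100%, and a value of 108.3% still does not show what was taken.

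**The log is self-report.** It covers offsite doses, is unsupervised, and neither document says that its counts reach the database. This stands too, so its use in the fix is conditional.

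**The denominator is probably meant to be exposure.** A reader might infer that compliance is misstated in both directions, because time on study would take in the off-drug follow-up. The documents do not support that as the plan's rule. The same parenthesis says the days are for duration of exposure, and the 5.2.9 formula with last dose as the event equals 5.2.11. The 85.7% appears only if the qualifier is ignored. What remains is a label and a cross-reference that do not fit.

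**Drug exposure is also measured directly.** Total and unbound concentrations are taken at Weeks 4 and 12 (SAP 5.11.3.1), and the Week 12 predose value is correlated with the change in uptake (SAP 5.11.3.4). This limits the consequence, although samples at two steady-state visits do not count missed home doses and cannot show missed placebo doses.

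**Conclusion.** The zero rule should be changed. Its direction is certain: it leaves compliance correct or overstates it. Its size depends on how many tablets remained. Under the 56-tablet assumption, half a bottle remaining turns 83.3% into 100%, and a wholly untaken third bottle turns 66.7% into 100%. How often this would happen cannot be judged from the documents.

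The consequence is confined to a descriptive table. A reader might go further and infer that poor adherers are the ones who keep their bottles, so that the rule would conceal the reason for a flat PET result. The documents say nothing about who fails to return bottles. Compliance does not enter the primary analysis, and plasma concentrations give independent evidence on exposure. The supportable statement is that the adherence table could not be relied on for participants with missing counts.

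The denominator wording is an inconsistency to correct, not a demonstrated downward error.

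**What to change.** In SAP 5.2.12, before database lock:

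1. Remove the substitution of zero. Work by dispensing interval. If the returned count is missing, take tablets used from the dosing log for that interval, provided its dose counts are captured in the database. Otherwise set that interval's compliance to missing, remove its expected tablets from the denominator, and report by arm the number of participants affected.
2. Replace the days-on-study wording and the reference to 5.2.9 with days of exposure per Section 5.2.11.

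The second change leaves two conventions in place that the sponsor should state knowingly. Breaks are not removed from exposure, so a 14-day interruption with every other dose taken reads (70 × 2)/168 = 83.3%. For exposure, "If date of last dose is not present, the date of completion/termination will be imputed as the date of last dose"; if that date is Day 98, a full adherer again reads 85.7%.

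The cost is a few sentences, some programming by interval, and a check on whether log data are in the database. Some participants will have lower or missing compliance, which reflects what is actually known about them.
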